### **Revision History**

Revision	Version Date	Revision Details	Consent
#			Revision
	Mar 13, 2020	Original to FDA	n/a
	Apr 08, 2020	In response to FDA IR April 6 2020	n/a
	Apr 09, 2020	In response to FDA IR April 8 2020	n/a
	am	Additional edits:	
		
 
Revise Section 8 – Tests and procedures to reflect more
 
	
		frequent follow-up and increased research related sample	
		collection	
		
 
Edits through-out to reflect a single dose of rituximab and a
 
	
		single dose of FT596	
	Apr 09, 2020	In response to the FDR IR April 9 2020 – original version to	
	pm	CPRC	
	May 20, 2020	CCPM and general edits before IRB submission:	Initial
		• Synopsis, Section 3, Section 8, Section 12.1: make consistent	consent
		throughout protocol that rituximab is given 2-3 days prior to	
		F 1596, clarify only on dose of F 1596 is given in this study	
		• Schema, Synopsis, Section 6.4, Section 10.4, Section 12.4.	
		day of transplant not day of ET506	
		• Schema, Section 3, Sections 6,2 and 6,3, Section 8 and other	
		
 
Schema, Section 5, Section 5 0.2 and 0.5, Section 6 and other places: add a +/- 1 day window for Day 7 and Day 30 FT596
 
	
		infusion to permit some flexibility of scheduling for individual	
		patients	
		
 
Section 6.1.2 – update FT596 administration language to be
 
	
		consistent without other Fate protocols	
		• Section 7.2 Schema, Section 8.1 – add a Day 21 timepoint for	
		disease reassessment, vascular access assessment, etc. for	
		Component 1 to permit rituximab administration on Day 28 for	
		Day 30 FT596.	
		• Section 7.2 – add recommended IV hydration to reduce the risk	
		of DMSO related toxicity	
		
 
Section 7.3 – add monitoring of CRP and ferritin 3 times per
 
	
		week until resolution in the event CRS is diagnosed (with	
		caveat missed testing will not be a deviation as patients maybe	
		outpatient)-	
		
 
Section 8.1 – remove KPS row, add row for concomitant
 
	
		medications, vascular access assessment, testing associated with CRS and neurotoxicity	
		
 
Section 8.2 – refine research related samples and collection
 
	
		schedule	
		
 
Section 10.7 – update expedited reporting table to reflect
 
	
		Advarra as IRB of record and other updates	
		Delete Appendix I as Karnofsky PS not assessed (not part of	
		eligibility	
		
 
Other minor edits and clarifications through-out (tracked)
 
	

Revision	Version Date	Revision Details	Consent
#			Revision
1	Oct 29 2020	
 
Synopsis, schema, Sections 3-5, Section 8 - General update to permit study consent/registration and enrollment after HCT
 
Section 7.3 - clarify IL-6 sample collection and update Table 1 tocilizumab administration guidelines for hypotension refractory to fluid boluses, add Actemra® (tocilizumab) prescribing info to References
 
Section 8.2 - add Day 28 CRP and ferritin, Add research samples at 3, 6, and 12 month post-transplant follow-up
 
Section 8.2 - delete the row for chimerisms from the research samples - update the 6 ml green top tubes with a new footnote 1 with instructions to use part of the green tops for PK samples (replacing chimerisms as testing done at the institutional level would not provide meaningful results).
 
Section 8.2 - move PRA anti-HLA antibodies testing from prior to transplant to prior to FT596, add baseline safety samples for Fate
 
Section 4.3 - correct wording "no requirement" for systemic immunosuppression during FT596 treatment period
 
Delete Section 5.3 and move wording to Section 5.2
 
Minor edits to Section 8.1 removing unnecessary con med assessment time points and updating footnote 6 to match the schedule of vital sign monitoring to Section 6.1.2
 
Section 10.7 - Delete row in required reporting table for DLT and SR reporting to the SAE coordinator as now automatically receives notification via OnCore.
 
Other minor edits and clarifications
 
	Yes
2	Nov 30 2020	
 
Synopsis, Section 6.1, Section 9.2 and throughout protocol clarify rituximab may be Rituxan or any FDA approved biosimilars
 
Synopsis, Schema, Section 6, Section 8 – permit a +3 day window from the targeted FT596 targeted administration (Day 30 or Day 7 post-transplant) for the rituximab/FT596 "package". Rituximab or an FDA approved biosimilar administration remains at 48-72 hours prior to the day of the planned FT596 infusion.
 
Other minor edits and clarifications
 
	yes

### Key Abbreviations

Abbreviation	Definition
ABW	actual body weight
ADL	activities of daily living
AE	adverse event
Auto-HSCT	autologous hematopoietic stem cell transplant
CAR	chimeric antigen receptor
CFR	Code of Federal Regulations
CNS	central nervous system
CRS	cytokine release syndrome
CTCAE	Common Terminology Criteria for Adverse Events
DLCO	diffusing capacity of the lungs for carbon monoxide
DLT	Dose limiting toxicity
eCRF	electronic case report form
EOT	end of treatment
FDA	Food and Drug Administration
GCP	Good Clinical Practice
GvHD	graft-versus-host disease
HCT	hematopoietic cell transplantation
HSCT	hematopoietic stem cell transplantation
IB	Investigator's Brochure
ICH	International Conference on Harmonisation
IL-15RF	IL-15 receptor alpha fusion protein
IND	Investigational New Drug
IPI	International Prognostic Index
IRB	Institutional Review Board
IV	intravenous
LTFU	long-term follow-up
NCI	National Cancer Institute
NHL	non-Hodgkin lymphoma
NK	natural killer
OS	overall survival
PBMC	peripheral blood mononuclear cell
PD	progressive disease
PFS	progression free survival
PFT	pulmonary function test
RECIST	Response Evaluation Criteria in Solid Tumors
rhIL-15	Recombinant human interleukin-15
SAE	serious adverse event
SD	stable disease
SOC	standard of care
SR	stopping rule
TITE-CRM	time-to-event continual reassessment method
TRM	treatment related mortality
ULN	upper limit of normal

### **Protocol Synopsis**

#### FATE FT596 with Rituximab as Relapse Prevention in High Risk Patients after Autologous Hematopoietic Stem Cell Transplantation for Non-Hodgkin Lymphoma

Study Design:	This is a Phase I multi-center study to evaluate the safety of FT596 when given with rituximab as relapse prevention in patients who have undergone an autologous hematopoietic stem cell transplant (auto-HSCT) for diffuse large or high-grade B cell lymphoma.
	For the majority of participants, this study is presented to the patient and consent is signed at the time consent for the autologous transplant is obtained. Research related samples are collected prior to the start of conditioning on any consented patient. Alternatively, a patient may be consented and enrolled after the transplant provided the patient can begin treatment within their assigned window.
	The transplant procedures and follow-up are conducted per institutional standard of care. Participation in this study does not affect or impact the transplant, supportive care, and subsequent post-transplant care, except that, if post-transplant radiation therapy is planned, it must be delayed until after Day 100.
	FT596 is comprised of allogeneic natural killer (NK) cells expressing a CD19-targeted chimeric antigen receptor (CAR), a high-affinity non cleavable CD16 receptor (hnCD16), and an interleukin (IL)-15/IL-15 receptor alpha fusion protein (IL-15RF). FT596 is an off-the-shelf cellular product and expected to be uniform in composition. The mechanism of action is targeting B-cell tumor cells through direct cytotoxicity, CAR-mediated targeting of CD19 as well as through antibody-dependent cellular cytotoxicity (ADCC) in combination with rituximab for a dual-targeting approach.
	This study uses a single dose of the investigational product FT596 in the early post-transplant period. Rituximab or an FDA approved by biosimilar including Rituxan®, Truxima®, and Ruxience™ is given 2- 3 days prior to FT596. The goal of this study is to 1) establish a maximum tolerated dose (MTD) of FT596 when given 30 days after transplant and 2) to confirm the MTD and safety of giving a single dose of FT596 at Day 7 post-transplant starting at one dose level below the MTD identified at Day 30.
	Component 1: Identify the maximum tolerated dose (MTD) of FT596 when given as a single dose
	Up to three FT596 dose levels are planned for Day 30 administration (with a +3 day window): (Dose Level 1: 9x10  cells/dose, Dose Level 2: 3x10  cells/dose, Dose Level 3: 9x10  cells/dose with a Dose Level -1: 3x10  cells/dose tested only if DLT at DL1).The maximum tolerated dose will be determined by using a modified continual reassessment method (CRM).
	Patients are enrolled in cohorts of 3 starting at Dose Level 1. A minimum of 28 days will separate each cohort. For Dose Level 1 a minimum of 28 days will separate each patient to assess for dose limiting toxicity (DLT). In subsequent cohorts, the 1 st and 2 nd patient will be separated by at least 28 days and at least 14 days will separate the 2 nd and 3 rd patient.
	Each new cohort of three patients will be sequentially assigned to the most appropriate dose based on the updated toxicity probabilities under the continuous reassessment method (CRM), and the MTD will be identified when the total sample size of 18 is exhausted or 6 patients are sequentially enrolled at the same dose.
	Dose limiting toxicity is defined as any of the following events within 28 days of FT596 dosing based on
	
 
Grade 4 hematologic toxicity lasting > 7 days (not including lymphopenia)
 
Grade 4 non hematologic toxicity
 

	
 
Grade ≥ 3 FT596 Infusion Related Reaction
 

	
 
Grade 2 acute GVHD that requires steroid therapy >7 days or progression after 3 days of steroids or has partial response after 14 days of treatment
 
Grade ≥3 acute GVHD
 

	
 
Grade 4 cytokine release syndrome (CRS)
 
Grade 3 CRS that does not resolve to < Grade 2 in 72 hours
 

	Grade 3 organ toxicity involving vital organs; cardiac, central nervous system and pulmonary which lasts longer than 7 days including Grade 3 Investigations (laboratory values) of any duration that discrete demonstrate the vital encoded.
	
 
Any Grade 3 non-hematological toxicity that does not resolve to ≤Grade 2 within 72 hours; excepting Grade 3 renal and hepatic toxicity which may take up to 7 days to resolve to ≤Grade 2
 

	Note: Once enrollment is completed for Component 1, enrollment will be suspended. A summary for Component 1, including safety data (summary of DLT and SR events) will be provided to the FDA for review. Only after receiving their permission will Component 2 begin enrollment. If permission is not received, the study will end.
	Component 2: To determine the safety of FT596 when given at Day 7 based on the MTD from Component 1.
	Component 2 will use a similar design but identifies the MTD of FT596 when given as a single dose at Day 7 (with a +3 day window) post-transplant. Up to two dose levels of FT596 are planned (one dose level below the MTD from Component 1 and the MTD from Component 1). Any two sequential dose levels of FT596 may be included: Dose Level -1: 3x10  cells/dose, Dose Level 1: 9x10  cells/dose, Dose Level 2: 3x10  cells/dose, Dose Level 3: 9x10  cells/dose.
	The maximum tolerated dose will be determined by using a modified continual reassessment method (CRM). Patients are enrolled in cohorts of 3 starting at one dose level below the MTD of Component 1 (MTD-1). Only the MTD-1 and the MTD of Component 1 will be tested. A minimum of 28 days will separate each cohort. For the 1 st cohort a minimum of 28 days will separate each patient to assess for dose limiting toxicity (DLT). In subsequent cohorts, the 1 st and 2 nd patient will be separated by at least 28 days and at least 14 days will separate the 2 nd and 3 rd patient. Each new cohort of three patients will be sequentially assigned to the most appropriate dose based on the updated toxicity probabilities. The MTD will be identified when the total sample size of 18 is exhausted or 6 patients are sequentially enrolled at the same dose.
	The DLT events for Component 2 are the same as in Component 1 except for the addition of: • Non-engraftment by Day 28 post-transplant
	
 
Monitoring guidelines for excessive toxicity (Stopping Rule events) Component 1 and Component 2 (ONLY POST FT596 EVENTS COUNT HERE))
 
The following events occurring after the FT596 infusion are measures of excessive toxicity based on Day 0 as the Transplant Day). Each component is monitored separately.
 
Mortality by Day 100
 
Grade III-IV Acute GVHD by Day 100
 
Any Grade 4 FT596 Infusion Related Reaction
 
Any Grade 4 Dose Limiting Toxicity (DLT) event
 
Grade 4 Lymphopenia (<200 cells/uL) at Day 100
 
Engraftment failure by Day 28 (Component 2 only)
 

Study Products:	FT596 and rituximab (Rituxan or any FDA approved biosimilar)
Primary Objective:	The primary objective of this study is: Component 1: Establish a maximum tolerated dose (MTD) of FT596 when given 30 days after transplant. Component 2: Confirm the MTD and the safety of giving a single dose of FT596 at Day 7 post-transplant using one dose level below the MTD (MTD -1) or the MTD from Component 1.

Secondary Objectives:	
 
To evaluate the adverse events related to FT596 administered post auto-HSCT in combination with rituximab (Rituxan or an FDA approved biosimilar, e.g. Truxima and Ruxience).
 
To determine preliminary efficacy based on progression free survival (PFS) and relapse/progression at 12 months post auto-HSCT.
 
To determine the incidence of non-relapse mortality at 100 days and 1 year post auto-HSCT.
 

Objectives:	
 
To evaluate persistence of FT596 in blood after each FT596 infusion by immunophenotyping and PCR up to 1 year.
 
To assess the association of FT596 cell persistence with safety and anti-tumor activity.
 
To assess the association of baseline clinical and tumor characteristics with safety and response endpoints following administration of FT596.
 

Key Inclusion Criteria: (at time of consent/ screening)	
 
Diagnosis of diffuse large B cell lymphoma or aggressive (high-grade) B-cell lymphoma for which an autologous stem cell transplant is planned or recently completed
 
High risk for relapse defined as at least one of the below: 
 
Primary induction failure (no complete or partial remission at any point after diagnosis)
 
Initial remission duration < 12 months
 
Lack of complete metabolic (PET scan) response after 2-3 cycles of salvage chemotherapy
 
Evidence of c-myc and bcl-2 and/or bcl-6 re-arrangement (double hit or triple hit lymphoma)
 
Age-adjusted International prognosis index (IPI) 2-3 at relapse
 
 
 
Agrees to use adequate contraception (or evidence of sterility) at least 12 months after the last dose of rituximab.
 
Agrees and signs the separate consent for up to 15 years of follow-up (Long-term Follow-up study CPRC#2020LS052)
 
Provides voluntary written consent prior to the performance of any research related activities.
 

Key Exclusion Criteria: (at time of consent/ screening)	
 
Receipt of any investigational therapy within 28 days prior to the first dose of FT596 or planned use of an investigational therapy during the first 100 days after transplant
 
Planned post-transplant irradiation prior to Day +100
 
Seropositive for HIV, active Hepatitis B or C infection with detectable viral load by PCR
 
Body weight <50kg
 
Known allergy to the following FT596 components: albumin (human) or DMSO
 
Unable to receive rituximab
 

Post-HCT Eligibility Confirmation	
 
No life-threatening medical issues (i.e. ongoing Grade 4 adverse events) where, in the opinion of the treating investigator, use of FT596 is not in the patient's best interest.
 
No active uncontrolled infection.
 
Adequate organ function post-transplant including: 
 
alanine aminotransferase (ALT) and aspartate aminotransferase (AST) ≤5 x ULN (Grade 2 CTCAE v5)
 
total bilirubin ≤1.5 x ULN (Grade 1 CTCAE v5)
 
serum creatinine ≤1.5 x ULN (Grade 1 CTCAE v5)
 
oxygen saturation ≥93% on room air
 
 
 
For Day 30 dosing only – CBC requirement consistent with engraftment (ANC>500, platelet>20,000 without transfusion support within previous 7 days). There are no CBC parameters for Day 7 dosing.
 

Enrollment Plan:	Component 1: a maximum of 18 patients, but most likely 12 if toxicity is as expected Component 2: a maximum of 18 patients, but most likely 12 if toxicity is as expected
Accrual:	It is expected 12-18 patients could be enrolled per year with two sites.

#### **Study Schema**

Treatment may be given as an inpatient or outpatient – there is no study driven requirement for a hospital admission.

#### Component 1 - FT596 at Day 30 Post Transplant to Identify MTD

Consent*	HSCT	dz	eval XI				
Pre-HSCT period							
Transplant Day	0	+7 +2	21 +30	+60	+ 100	+180	+365

\* Alternatively consent/initial screening may be done after HSCT – refer to Section 5.

Schedule for disease assessment around Day +21 to allow for rituximab to be given on Day 28

FT596 at assigned dose\* Note a +3 day window is permitted for FT596 dosing (i.e. Day +31, Day +32 or Day +33)
 X Rituximab (Rituxan or an FDA approved biosimilar, e.g. Truxima and Ruxience) 375 mg/m^2 IV 2-3 days before FT596 (refer to Section 6.1 for details)

#### \*Dose Levels for Identification of MTD

Dose Level	FT596 Cells per Dose	Enrollment Plan
-1	3 x 10  cells	Tested only if Dose Level 1 has DLT
1 (start)	9 x 10  cells	Enroll 3 patients at Dose Level 1 with at least 28 days between each of the 3
2	3 x 10  cells	patients. Once the 28 day DLT assessment periods ends for all 3 patients,
3	9 x 10  cells	enroll the next cohort of 3 patients to the most appropriate dose based on the updated toxicity probabilities. A minimum of 28 days must separate the 1 st and 2 nd patients and a minimum of 14 days must separate the 2 nd and 3 rd patient within a cohort. The MTD is identified when the total sample size of 18 is exhausted or 6 patients are sequentially enrolled at the same dose.

**Component 1 dose limiting toxicity** is defined as any of the following events within 28 days after FT596 dosing based on CTCAE v5:

- Grade 4 hematologic toxicity lasting > 7 days (not including lymphopenia)
- Grade 4 non-hematologic toxicity
- Grade ≥3 FT596 Infusion Related Reaction
- Grade 2 acute GVHD that requires steroid therapy >7 days or progression after 3 days of steroids or has partial response after 14 days of treatment
- Grade ≥3 acute GVHD
- Grade 4 cytokine release syndrome (CRS)
- Grade 3 CRS that does not resolve to < Grade 2 in 72 hours
- Grade 3 neurotoxicity
- Grade 3 organ toxicity involving vital organs; cardiac, central nervous system and pulmonary that lasts longer than 7 days including Grade 3 Investigations (laboratory values) of any duration that indicate damage to vital organs.
- Any Grade 3 non-hematological toxicity that does not resolve to ≤Grade 2 within 72 hours; excepting Grade 3 renal and hepatic toxicity which may take up to 7 days to resolve to ≤Grade 2

# Component 1 monitoring guidelines for excessive toxicity (Stopping Rule events) occurring after the FT596 infusion based on Day 0 as the Transplant Day (ONLY POST FT596 EVENTS COUNT HERE):

- Mortality by Day 100
- Grade III-IV Acute GVHD by Day 100
- Any Grade 4 FT596 Infusion Related Reaction
- Any Grade 4 Dose Limiting Toxicity (DLT) event
- Grade 4 Lymphopenia (<200 cells/uL) at Day 100

#### NOTE: Component 2 may not begin until after the FDA gives permission to proceed (refer to Section 6.3) Component 2 - Safety of FT596 when given at Day 7 based on the MTD from Component 1

Consent* Pre-HSCT period	HSCT	XI						
Transplant Day	0	+7	+30	+60	+ 100	+180	+365	

\* Alternatively consent/initial screening may occur after HSCT – refer to Section 5

FT596 at assigned dose\* Note a +3 day window is permitted for FT596 dosing (i.e. Day +8, Day +9 or Day +10)
 X Rituximab (Rituxan or an FDA approved biosimilar, e.g. Truxima and Ruxience) 375 mg/m^2 IV 2-3 days before FT596 (refer to Section 6.1 for details)

#### \*Dose Levels for Identification of MTD at Day 7

Dose Level based on MTD from Component 1	Enrollment Plan
MTD – 1 Dose Level (Start)	Enroll 3 patients at Dose Level 1 with at least 28 days between each of the 3 patients. Once the 28 day DLT assessment periods ends for all 3 patients,
MTD	enroll the next cohort of 3 patients to the most appropriate dose based on the updated toxicity probabilities. A minimum of 28 days must separate the 1 st and 2 nd patients and a minimum of 14 days must separate the 2 nd and 3 rd patient within a cohort. The MTD is identified when the total sample size of 18 is exhausted or 6 patients are sequentially enrolled at the same dose.

**Component 2 dose limiting toxicity** is defined as any of the following events within 28 days after FT596 dosing based on CTCAE v5:

- Grade 4 hematologic toxicity lasting > 7 days (not including lymphopenia)
- Grade 4 non-hematologic toxicity
- Grade ≥3 FT596 Infusion Related Reaction
- Grade 2 acute GVHD that requires steroid therapy >7 days or progression after 3 days of steroids or has
  partial response after 14 days of treatment
- Grade ≥3 acute GVHD
- Grade 4 cytokine release syndrome (CRS)
- Grade 3 CRS that does not resolve to < Grade 2 in 72 hours
- Grade 3 neurotoxicity
- Grade 3 organ toxicity involving vital organs; cardiac, central nervous system and pulmonary that lasts longer than 7 days including Grade 3 Investigations (laboratory values) of any duration that indicate damage to vital organs.
- Any Grade 3 non-hematological toxicity that does not resolve to ≤Grade 2 within 72 hours; excepting Grade 3 renal and hepatic toxicity which may take up to 7 days to resolve to ≤Grade 2
- Non-engraftment by Day 28 post-transplant

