#### 1 Objectives

#### 1.1 Primary Objective

The primary objective of this study is:

Component 1: Establish a maximum tolerated dose (MTD) of FT596 when given 30 days after transplant and

Component 2: Confirm the MTD and safety of giving a single dose of FT596 at Day 7 post-transplant using one dose level below the MTD (MTD -1) or the MTD from Component 1.

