# NOTE: Component 2 may not begin until after the FDA gives permission to proceed (refer to Section 6.3).

Component 2 will use a similar design but identifies the MTD of FT596 when given as a single dose at Day 7 post-transplant. Up to two dose levels of FT596 are planned (one dose level below the MTD from Component 1 and the MTD from Component 1). Any two sequential dose levels of FT596 may be included: Dose Level -1:  $3x10^7$  cells/dose, Dose Level 1:  $9x10^7$  cells/dose, Dose Level 2:  $3x10^8$ cells/dose, Dose Level 3:  $9x10^8$  cells/dose.

The maximum tolerated dose will be determined by using a modified continual reassessment method (CRM). Patients are enrolled in cohorts of 3 starting at one dose level below the MTD of Component 1 (MTD-1). Only the MTD-1 and the MTD of Component 1 will be tested. A minimum of 28 days will separate each cohort. For the 1st cohort a minimum of 28 days will separate each patient to assess for dose limiting toxicity (DLT). In subsequent cohorts, the 1st and 2nd patient will be separated by at least 28 days and at least 14 days will separate the 2nd and 3rd patient. Each new cohort of three patients will be sequentially assigned to the most appropriate dose based on the updated toxicity probabilities. The MTD will be identified when the total sample size of 18 is exhausted or 6 patients are sequentially enrolled at the same dose.

Definitions of dose limiting toxicity and monitoring for excessive toxicity are found in Section 12. 4.

Follow-up (all patients): Direct study participation ends at 1 year post-transplant.

**Long-Term Follow-Up (any patient who received at least one dose of FT596):** After 1 year, follow-up will transfer to a separate long-term follow-up (LTFU) study (UMN CPRC #2020LS052) to continue the FDA's required 15 year follow-up after treatment with a genetically modified cell therapy. Participation in the LTFU study is mandatory as part of the inclusion criteria of this treatment study.

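### The Component 2 schema table names Dose Level 1 as the Day 7 start, where the plan intends one level below the Component 1 MTD

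*Combined protocol and SAP*

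**What the plan says.** The Component 2 dose table in the Study Schema has a first column headed "Dose Level based on MTD from Component 1". Its first row is labelled "MTD – 1 Dose Level (Start" and its second row is the MTD. The enrolment text beside these rows reads "Enroll 3 patients at Dose Level 1 with at least 28 days between each of the 3 patients".

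The Component 1 table in the same schema uses the same words, "Enroll 3 patients at Dose Level 1 with at least 28 days between each of the 3". They are correct there, because Component 1 does start at Dose Level 1.

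Elsewhere the Component 2 start is defined relative to the Component 1 result:

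- The Synopsis and Section 3 both describe Component 2 as "starting at one dose level below the MTD identified at Day 30".
- Section 3 adds "Patients are enrolled in cohorts of 3 starting at one dose level below the MTD of Component 1 (MTD-1" (the closing bracket falls outside the quote).
- The Synopsis and Section 3 limit the doses: "Only the MTD-1 and the MTD of Component 1 will be tested".
- The Component 2 primary objective in Section 1.1 names the same two doses: "using one dose level below the MTD (MTD -1) or the MTD from Component 1".

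Dose Level 1 is defined as 9x10^7 cells, including within the Component 2 descriptions in the Synopsis and Sections 3, 6.3 and 12.1.

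**The concern.** The table gives two different starts for the first Day 7 cohort. The row label moves with the Component 1 MTD; the enrolment text names a fixed dose. They agree for only one Component 1 outcome.

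The stake is the dose given to the first three patients treated at Day 7. Section 7 states that there are no clinical data for FT596. Section 12.1 allows that toxicity may be slightly higher at Day 7 and adds non-engraftment as a DLT. Starting one level down is the plan's protection against that. A site following the enrolment text literally could lose that step, or could treat patients at a dose Component 2 is not meant to test.

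**Working it through.** **Inputs.** Dose levels (Synopsis; Sections 3, 6.3 and 12.1): DL-1 = 3x10^7, DL1 = 9x10^7, DL2 = 3x10^8, DL3 = 9x10^8 cells. Component 2 tests two adjacent levels, the Component 1 MTD and the level below it. The Component 1 CRM is set up to pick one of three levels, DL1 to DL3 (Section 12.1).

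**Comparison.** For each Component 1 MTD, intended start = the level one below. Ratio = printed start (9x10^7) / intended start.

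| Component 1 MTD | Permitted pair | Intended start | Printed / intended | Printed / MTD |
|---|---|---|---|---|
| DL1 (9x10^7) | DL-1, DL1 | 3x10^7 | 9x10^7 / 3x10^7 = 3.0 | 9x10^7 / 9x10^7 = 1.0 |
| DL2 (3x10^8) | DL1, DL2 | 9x10^7 | 9x10^7 / 9x10^7 = 1.0 | 9x10^7 / 3x10^8 = 0.3 |
| DL3 (9x10^8) | DL2, DL3 | 3x10^8 | 9x10^7 / 3x10^8 = 0.3 | 9x10^7 / 9x10^8 = 0.1 |

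The printed dose is the upper member of the first pair, the lower member of the second, and absent from the third. It is the correct start in one of the three.

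**Check against Section 12.** The worked example for Component 2 in Section 12.1 starts at DL2, with skeleton values of 5% and 10% for DL2 and DL3. Table 2 in Section 12.2 simulates 3x10^8 and 9x10^8 only, with 6 + 6 = 12 patients per scenario and none at 9x10^7. A fixed DL1 start cannot produce that design.

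**Could Dose Level 1 mean the first level of Component 2?** The protocol never defines it that way, and its Component 2 text repeats the fixed 9x10^7 meaning.

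**Could this be a broken table?** The extracted text does not show whether the enrolment wording is one merged cell or belongs to the MTD-1 row. The sentence is complete, and under either layout it names the wrong dose. A similar carry-over occurs in Section 6.3, where the DLT list under the Component 2 heading opens by calling itself the Component 1 definition.

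**The case against.** The strongest reply is that this is an editorial slip with little practical risk. The correct start is in the adjacent row label, in the Synopsis and in Section 3. Section 6.3 refers to Section 3 for staggering, and the same Section 3 paragraph states the start. Patients are assigned to the currently enrolling treatment plan (Section 5.2), registration is centralized (Section 11.5), and Component 2 cannot open without FDA permission (Section 6.3). In none of the three cases above does the printed dose exceed the Component 1 MTD. In the DL3 case the error is on the cautious side. The Section 12 example is conditional on a DL2 start, so it does not by itself rule out a DL1 start.

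Most of this stands: the intent is recoverable, misdosing is unlikely, and the Section 12 material is supporting evidence only. It does not make the printed instruction right. Section 6.3, the treatment section, names the two planned levels without saying which comes first and cites Section 3 only for staggering. A site reader who sees the conflict must decide which text governs.

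The three-case count also leaves out an MTD of DL-1, which can be tested after a DLT at DL1. There is no lower level in that case, and the printed dose would be 9x10^7 / 3x10^7 = 3 times the MTD. Including it adds a mismatch.

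**Conclusion.** The concern holds. The enrolment text is wrong as written and contradicts its own table. Taken literally, it gives the intended start only if the Component 1 MTD is DL2, 0.3 times the intended start (and an untested dose) if it is DL3, and 3 times the intended start if it is DL1.

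This rests on Dose Level 1 keeping its stated meaning of 9x10^7 cells and on Component 1 selecting one of DL1 to DL3. The three cases are not equally likely. Table 1 in Section 12.2 has DL3 selected 100% of the time under expected toxicity, which is the case where the printed dose is outside the permitted pair. Those percentages describe MTD selection, not the risk of misdosing, and no such risk is estimated here.

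The intended design is sound. The point is a correction to an operative starting-dose instruction and should be made.

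**What to change.** In the Component 2 schema table, replace the reference to Dose Level 1 with *the MTD-1 dose level (one level below the Component 1 MTD)*. Add one sentence to Section 6.3 stating that the first cohort starts there. The table change is essential; the Section 6.3 sentence means a reader of the treatment section need not look elsewhere for the start.

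The cost is one phrase and one sentence at the next amendment. The enrolment pause for FDA review between components is a natural time to do it, and it should be done before Component 2 opens.
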